9.2.1. Inclusion criteria

Participants must meet all of the following inclusion criteria to be eligible for inclusion in the study:

- Women of any age who are currently or recently pregnant (recently pregnant defined as enrollment within 1 year of pregnancy outcome)
 - Only prospectively enrolled patients (i.e., women who are currently pregnant at enrollment) will be included in the main analysis population
- Consent to participate in this study and evidence of a personally signed and dated informed consent document indicating that the patient (or a legally acceptable representative) has been informed of all pertinent aspects of the study
- Authorization for her HCP(s) to provide data to the registry
- Exposed cohort only: Must receive at least one dose of CIBINQO at any time during pregnancy (from the DOC to pregnancy outcome) or prior to pregnancy (within 1 day prior to the DOC).
- Comparator cohort only: Must have a diagnosis of moderate-to-severe AD at any time prior to pregnancy outcome.

9.2.2. Exclusion criteria

Participants will be excluded from the registry if they do not meet the inclusion criteria listed above.

Some participants included in the registry may be excluded from the statistical analysis (details in Section 9.7).

PFIZER CONFIDENTIAL Page 20 of 67

9.2.3. Participant recruitment and retention

9.2.3.1. Participant recruitment

An active, targeted, multi-pronged recruitment campaign will be employed to recruit participants for the registry. The campaign will focus on pregnant women, patients with moderate-to-severe AD, patients using CIBINQO or other products for the treatment of moderate-to-severe AD, obstetric HCPs, HCPs who are likely to treat patients with moderateto-severe AD, and HCPs who are likely to prescribe CIBINQO. Obstetric HCPs and HCPs who are likely to treat patients with moderate-to-severe AD may be identified via HCP directories and/or professional associations. Pregnant women, patients with moderate-tosevere AD, and patients using CIBINQO may be identified through patient support groups and external data sources, such as pharmacy/medical claims or electronic medical records. The sponsor's existing infrastructure for distributing CIBINQO and supporting stakeholders (e.g., Pfizer Med Info and the patient assistance program) may be leveraged to identify HCPs who are known to prescribe CIBINQO or a comparator medication and pregnant women who are using CIBINQO or a comparator medication.

A multi-modal approach will be used to deliver registry education and recruitment materials to targeted HCPs and patients. This approach involves direct-to-HCP outreach as well as online and print advertising directed to both HCPs and patients. In addition, stakeholders may be identified and provided with information regarding the registry via telephone through the Medical Information Contact Center and the patient assistance program.

Direct-to-HCP outreach will be achieved by delivering recruitment materials to targeted HCPs via email, fax, and/or hardcopy mail. HCPs can use any approach to identify potentially eligible participants. In addition, the Sponsor's representatives may provide registry education and recruitment materials to HCPs in person. HCPs will be asked to identify potential registry participants and encourage their participation by informing them about the registry and providing them with the patient-directed registry recruitment materials. The VRCC will be available to answer questions from those who are potentially interested in participating in the registry.

Information regarding the registry and the registry recruitment materials will also be available online. A registry-specific website will be developed at http://cibinqopregnancyregistry.com/, where all recruitment materials will be available for download. This website will be accessible through the CIBINQO product website and discoverable in any internet browser by performing a search related to pregnancy and CIBINQO, abrocitinib, and/or moderate-to-severe AD. Information regarding the registry and/or a link to the registry website will be available on websites that aim to provide medical information to pregnant women, including but not limited to the following websites:

- FDA listing of pregnancy registries on www.fda.gov, www.clinicaltrials.gov
- Society for Maternal-Fetal Medicine listing of registries
- PPD website

A web-based interface compatible with both computers and mobile devices will also be developed to improve information accessibility and enable broader participation. The webbased interface will comply to the standards outlined by the Americans with Disabilities Act. As deemed necessary, online advertisements on social media sites or other relevant websites (e.g., professional association websites or websites commonly visited by pregnant women) or applications may be used to inform potential participants of the registry.

Various print materials will also be used to provide information related to the registry and to facilitate recruitment. The CIBINQO prescribing information provides registry information including contact information. Information related to the registry may also be directed to HCPs via announcements/publications in relevant professional journals/newsletters or presentations/exhibits at relevant professional meetings. As deemed necessary, print advertisements in newspapers or magazines with targeted patients among their readership may be used to direct potential participants to the registry, and recruitment materials may be distributed to locations commonly frequented by targeted patients (e.g., ultrasound clinics, gynecologic surgery centers).

In addition to the registry information in the product label, educational materials designed to elicit interest in registry participation will be developed. All messaging will be aligned with the product label. Materials may include:

- An information sheet and/or brochure that will briefly describe the registry purpose and procedures, including the incentives for participation
- Information on how to access the registry web-based/mobile application
- Registration form and sample participant consent form
- Prescribing information
- Participant consent-to-contact card (this card enables the VRCC to contact the potential participant and provide additional information about the registry)

Additional details on study recruitment, such as the specific virtual recruitment initiatives (i.e., Everyday Health), will be described in a separate Recruitment Plan.

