9.4. Data sources

All data will be collected via data collection forms. Table 2 provides a summary of the data collection process, including the forms that will be used to collect the data, the timing for completion of each form, the potential reporters or sources of the data, and the types of data that will be collected.

Data Collection Form	Data Sources/Reporters	Timing of Completion	Data Collected
Registration Form for Participants	Participant	Enrollment	 Registration information, including eligibility criteria Maternal demographic characteristics
			• Maternal pre-pregnancy anthropometrics
Registration Form for HCPs	Obstetric HCP and prescriber, if needed	Enrollment	• Registration information, including eligibility criteria
			 Maternal obstetrical history
			• Family history of congenital malformations
			 AD disease information Baseline pregnancy information

Table 2. Summary of Data Collection Process

Data Collection Form	Data Sources/Reporters	Timing of Completion	Data Collected
Pregnancy Information Form	Obstetric HCP and prescriber, if needed	Enrollment, end of 2 nd trimester ^a , and EDD/pregnancy outcome ^a	 Ongoing pregnancy information Maternal exposures during pregnancy
Pregnancy Outcome Form	Obstetric HCP and pediatric HCP, if needed	EDD/pregnancy outcome	 Pregnancy outcome information AD disease information
Infant Outcomes Form	Pediatric HCP	4 and 12 months after delivery	• Infant outcome information at 4 and 12 months
Targeted Follow-up Form	Obstetric, pediatric, or other HCP	Any time after pregnancy outcome	• Targeted follow-up information

 Table 2.
 Summary of Data Collection Process

AD = a topic dermatitis; EDD = estimated date of delivery; HCP = healthcare provider.

a Obtain updated information since the previous contact.

The following data will be collected:

Registration Information (reported by the participant)

- Date of first contact with registry
- Date of consent (enrollment)
- Recruitment source(s)
- Minimum data for assignment to a study cohort, including:
 - Pregnancy status
 - o Diagnosis (AD) information
 - Exposure information
 - Prior enrollment (in this registry) status
- Minimum data for assignment to a study cohort (reported by HCP), including:
 - Pregnancy status
 - Diagnosis information
 - Exposure information

Maternal Demographic Characteristics (reported by the participant)

- Date of birth
- Ethnicity
- Race
- Education

Maternal Pre-Pregnancy Anthropometrics (reported by the participant)

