9.7. Data analysis

9.7.1. Analysis population

To provide valid effect estimates, the analysis population may differ from the population of women enrolled in the registry. The subset of registry participants included in the analysis will include women who:

- Have the minimum data required for determining inclusion/exclusion into one of the study cohorts
- Have sufficient data either submitted or confirmed by an HCP (i.e., an HCP must submit or confirm the data used to define the eligibility criteria)
- Have a diagnosis of moderate-to-severe AD
- Are prospectively enrolled (i.e., currently pregnant at enrollment)
- Are not exposed to teratogens or investigational medications during pregnancy
- Are not multiple gestation pregnancies for the analyses of preterm birth, SGA, and postnatal growth deficiency

Within each cohort, the baseline characteristics of those included in the analysis population will be compared with those excluded from the analysis population to evaluate potential differences between the population enrolled in the registry to the analysis population.

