Spontaneous abortion (SAB)	SABs among women with pregnancy outcome data who are enrolled (and exposed, if applicable based on cohort) prior to 20 gestational weeks	Women with pregnancy outcome data who are enrolled (and exposed, if a pplicable based on cohort) prior to 20 gestational weeks				
Stillbirth	Stillbirths a mong women with pregnancy outcome data	Women with pregnancy outcome data				
Elective termination	Elective terminations among women with pregnancy outcome data	Women with pregnancy outcome data				
Preterm birth	Singleton preterm live births without MCMs among women with pregnancy outcome data who are enrolled (and exposed, if applicable based on cohort) prior to 37 gestational weeks	Singleton live births without MCMs among women with pregnancy outcome data who are enrolled (and exposed, if a pplicable based on cohort) prior to 37 gestational weeks				

Table 6.Calculation of Outcome Proportion

Outcome	Numerator	Denominator
Small for gestational age (SGA)	Singleton live births without MCMs who are SGA among women with pregnancy outcome data	Singleton live births without MCMs with weight data a mong women with pregnancy outcome data
Postnatal growth deficiency (at 4 and 12 months)	Singleton infants without MCMs who were not born preterm or SGA with postnatal growth deficiency based on weight/length/head circumference among infants with weight/length/head circumference data at the time point	Singleton infants without MCMs who were not born preterm or SGA with weight/length/head circumference data at the time point
Infant developmental delay (at 4 and 12 months)	Infants without MCMs who were not born preterm with developmental deficiency in a particular category among infants with developmental milestone data for the category at the time point	Infants without MCMs who were not born preterm with developmental milestone data for the category at the time point

 Table 6.
 Calculation of Outcome Proportion

MCM = major congenital malformation; SAB = spontaneous abortion; SGA = small for gestational age.

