9.7.4. Subgroup and sensitivity analyses

If sample size permits, subgroup analyses will be conducted that consider the timing of exposure (earliest trimester of exposure), extent of exposure (cumulative dose during pregnancy or relevant exposure window), number of systemic therapy exposures during pregnancy (1 or \geq 1), and maternal age group at conception (<18, 18 to <35, 35 to <45, and \geq 45 years). The analysis of MCM will be stratified by earliest trimester of exposure, with a primary focus on exposure during the first trimester.

Sensitivity analyses will also be conducted to examine the extent to which changes in certain methods or assumptions affect the results. The sensitivity analyses may include, but are not limited to:

- Applying a stricter definition of prospective enrollment to the analysis of MCM. For this analysis, women who enroll or make initial contact with the registry prior to diagnostic prenatal testing will be considered prospectively enrolled, and women who enroll or make initial contact with the registry after diagnostic prenatal testing, regardless of the results, will be considered retrospectively enrolled.
- Accounting for the correlation between previous and subsequent pregnancies in the same woman and multiple gestation pregnancies using mixed models in the analysis of the outcome.
- Including the propensity score and a variable for treatment in an unweighted generalized linear model using a binomial family and a log (RR) link to test the robustness of IPTW.
- Applying inverse probability of censoring weights to account for potential informative censoring due to differential loss to follow up.

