9.9. Strengths and limitations of the research methods

Prospectively pregnancy registries offer several advantages over retrospective primary data collection studies and secondary database studies. The prospective design mitigates the potential for recall bias, a bias that may be introduced in retrospective primary data collection studies. Additionally, this prospective registry offers the potential to capture rich patient information that would not be captured in secondary databases. Critical data are provided directly from the HCPs and participants, including information that may not be routinely captured in medical records. This direct capture of data can minimize the potential for exposure, outcome, and covariate misclassification.

The general limitations of pregnancy registries with voluntary participation are well known, and these will apply to this study as well. One key limitation of the study is the limited size of the population of pregnant women expected to be exposed to CIBINQO during pregnancy. To maximize recruitment and retention, a multi-modal approach will be used to deliver registry education and recruitment materials to targeted HCPs and patients. The registry's recruitment and retention strategies will be flexible and will be continuously assessed. Based on these assessments and feedback form the SAC, the registry's recruitment and retention strategies will be adjusted as needed to maximize registry participation.

Another key limitation of the registry, due to the voluntary nature of participation, relates to representativeness. Since participation in the registry is voluntary, the pregnant women who voluntarily enroll in the registry may not be representative of the overall target population of pregnant women with moderate-to-severe AD in the US. This could introduce selection bias and affect the generalizability of the results. To minimize the potential for selection bias, a multi-faceted recruitment strategy will be employed.

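### Prospective enrolment rests on pregnancy status alone, so a termination already arranged, or arguably a loss already diagnosed, can be counted as a prospective event in the main analysis

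*Protocol*

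**What the plan says.** Protocol 9.2.1 sets the rule for the main analysis: "Only prospectively enrolled patients (i.e., women who are currently pregnant at enrollment) will be included in the main analysis population". Section 9.7.1 repeats it as a condition of the analysis population. Section 9.2.2 adds no exclusion beyond the inclusion criteria, and no criterion asks whether the outcome of the pregnancy is already known or decided.

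Table 6 (9.7.2) defines the numerators. For SAB it is "SABs among women with pregnancy outcome data who are enrolled (and exposed, if applicable based on cohort) prior to 20 gestational weeks". For elective termination it is "Elective terminations among women with pregnancy outcome data", with no condition on when the woman enrolled. Stillbirth has none either.

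Section 9.7.4 lists, among possible sensitivity analyses, "Applying a stricter definition of prospective enrollment to the analysis of MCM". There, women who enrol or first make contact after diagnostic prenatal testing are treated as retrospective. No such analysis is listed for SAB, stillbirth or elective termination.

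On recruitment, 9.2.3.1 states that, where deemed necessary, "recruitment materials may be distributed to locations commonly frequented by targeted patients (e.g., ultrasound clinics, gynecologic surgery centers"). Section 9.9 says: "To minimize the potential for selection bias, a multi-faceted recruitment strategy will be employed". It also discusses left truncation, but not entry of women whose outcome is already determined. Recruitment source is collected at registration (9.4). Its only stated use is to assess and adjust recruitment (9.2.3.3).

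**The concern.** Prospective enrolment is meant to ensure that entry does not depend on the outcome. For elective termination, pregnancy status alone does not do that: a woman with a scheduled procedure is still pregnant, can self-enrol by app or phone, and becomes an event with almost no time at risk. This is selection on the outcome rather than late entry, so adjusting for gestational age at enrolment does not remove it.

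The protocol recognises the same problem for MCM, where prior knowledge from testing is the reason for the stricter definition. It does not carry the idea over to the outcomes for which prior knowledge is most direct.

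The crude proportions of these outcomes in each cohort are part of the primary objective (section 8), and their comparison is the secondary objective. Women entering with a determined loss raise the proportions. If they enter equally in both cohorts, they also dilute a true increase in risk.

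**Working it through.** **Inputs from the protocol.** Reference prevalence: SAB 11.8%, elective termination 18.6% (Table 3). Precision method: Wilson 95% half-width (9.5.2). Enrolment: 200 or 364 women per cohort, with 10% excluded from analysis (9.5.2).

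**Inputs assumed.** f is the share of counted women who enter with the outcome already determined. The documents give no value; the range used is 1–10%. g is the share of SAB risk still ahead at enrolment, also assumed.

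**1. The plan's own figures.** The smallest n with z·√(p(1−p)/n + z²/(4n²)) / (1 + z²/n) ≤ 0.03, z = 1.96, is 446 for p = 0.118 and 645 for p = 0.186. Both match Table 3, so no tabulated figure is in question here.

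**2. Does the text admit these women?**
- Termination arranged, not yet performed: the woman is pregnant, so she meets 9.2.1 and 9.7.1 and is counted in Table 6. This is clear.
- Demise diagnosed, not yet expelled: Table 1 defines SAB as fetal loss or expulsion, and section 11 includes missed abortion under SAB. On that reading the outcome has occurred, and 9.5.2 treats an outcome before enrolment as retrospective. But the protocol never says whether diagnosis or expulsion dates the outcome. This is ambiguous.

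**3. Upward shift.** Observed proportion = f + (1 − f)p.

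| f (assumed) | SAB, p = 11.8% | Elective termination, p = 18.6% |
|---|---|---|
| 1% | 12.7% | 19.4% |
| 2% | 13.6% | 20.2% |
| 5% | 16.2% | 22.7% |
| 10% | 20.6% | 26.7% |

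For example, 0.05 + 0.95 × 0.118 = 0.162. Table 3 gives the termination reference a live-birth denominator, whereas Table 6 uses women. Read as a ratio, 18.6% is 0.186/1.186 = 15.7% of live births plus terminations, and f = 2% and 5% then give 17.4% and 19.9%.

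At f = 5% the SAB shift is 4.4 points. With 364 × 0.9 ≈ 328 analysed women per cohort, the Wilson half-width at 11.8% is 3.5 points; with 200 × 0.9 = 180 it is 4.7. So the shift exceeds the sampling error at the larger size and not at the smaller. At f = 2% the shift (1.8 points) is below both. In women, 2% and 5% of 328 are about 7 and 16.

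**4. Opposing shift from left truncation.** If a share g of SAB risk remains, expected SAB = pg / (1 − p(1 − g)). For g = 75%, 50% and 25% this is 9.1%, 6.3% and 3.2%. The f that brings it back to 11.8% is p(1 − g) = 2.95%, 5.9% and 8.85%. With g = 50%, f = 2% gives 8.1% and f = 5% gives 11.0%.

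**5. Relative risk for SAB, equal f in both cohorts.** RR = (f + (1 − f)·p·RR₀) / (f + (1 − f)·p), where RR₀ is the true RR.
- RR₀ = 1: stays at 1.
- RR₀ = 2, f = 2%: 0.2513/0.1356 = 1.85.
- RR₀ = 2, f = 5%: 0.2742/0.1621 = 1.69.

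**The case against.** The recruitment sentence is permissive: material may go to such sites where deemed necessary, the sites are examples, and details are left to a separate Recruitment Plan. That a pregnant woman at a gynecologic surgery center is probably there for a termination or evacuation is an inference the protocol does not state. For ultrasound clinics the inference is weak. Section 9.3.3 relies on first-trimester ultrasound for dating, so these clinics can reach women early, which 9.9 wants in order to limit left truncation. All of this stands. The root of the problem is the definition of prospective enrolment, and it exists whatever the recruitment site.

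A reader might infer that comparators depend more on general placements, so that contamination falls on one cohort. At f = 5% in one cohort only, a null SAB RR would become 1.37 (exposed) or 0.73 (comparator). The documents do not support that scenario: 9.2.3.1 says sponsor infrastructure may also be used to identify women using a comparator medication, and it targets patients with atopic dermatitis and their providers generally.

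Eligibility data must be submitted or confirmed by a provider (9.7.1). That confirms pregnancy, not whether a termination has been arranged. Enrolment and outcome dates, prenatal test results and the reason for termination are collected (9.4), so very short intervals could be flagged later. That is only a proxy for what was known at first contact.

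Finally, the sensitivity list is open-ended, and a rerun by recruitment source could sit in the SAP. True, but the enrolment question cannot: status not captured at entry cannot be reliably recovered at analysis.

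**Conclusion.** The definitional gap holds. It is clear for elective termination and ambiguous for SAB, because the protocol does not say when a diagnosed loss counts as having occurred. The primary MCM analysis among live births is not affected.

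The size is unknown. Under assumed shares of 2–5%, and taking the 11.8% reference as the true value, SAB would read 13.6–16.2%, and a true SAB RR of 2 would read 1.85–1.69 if both cohorts were equally affected.

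A reader might go further and conclude that the plan inflates these proportions. The documents do not support that: left truncation lowers them, and depending on how much risk remains at enrolment, a share of roughly 3–9% would be needed merely to return to the reference. The net direction is open. Two opposing biases of unknown size do not make the estimate sound, however, and a correction for left truncation, which 9.9 says may be applied, would leave the upward part in place.

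**What to change.** 1. Add one question at enrolment: before first contact with the registry, had a loss been diagnosed or a termination scheduled?
2. Extend the stricter-definition analysis in 9.7.4 to SAB, stillbirth and elective termination, treating women who answer yes as retrospectively enrolled. State in 9.3.2 or 9.7.1 that a loss diagnosed before enrolment is an outcome occurring before enrolment.
3. Repeat these three outcomes by recruitment source, which is already collected.
4. In 9.2.3.1, drop gynecologic surgery centers as an example site. Ultrasound clinics may stay, because they support early enrolment and the new question covers the risk there.

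The cost is one extra enrolment question, short wording changes, one extra analysis run and possibly a few fewer analysed women. Item 1 should be in place before enrolment starts.
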